4.3.1 Screening Phase

The Screening Phase will range from a minimum of 3 days to a maximum of 42. The purpose of the Screening Visit is to ensure that the appropriate patients are entered into the trial. The investigator will determine that the patient meets eligibility criteria and will collect demographic and medical data presenting a full characterization of the patient. It is estimated approximately 138 subjects will enter this phase of the trial.

Please refer to the Schedule of Assessments/Time & Events for details on Screening Procedures.

4.3.2 Randomization Phase

Subjects who are determined to be eligible for the study will enter the Randomization Phase. Subjects will receive placebo (QD) or troriluzole (140 mg QD). Dosing will continue for 8 weeks. Subjects will return to the clinic two weeks after discontinuing study medication for a follow-up safety visit. Subjects completing the Randomization Phase will be offered approximately 48 weeks of open-label treatment as long as the PI believes open-label treatment offers an acceptable risk-benefit profile.

[figure not shown]
• Subjects should take their medication in the mornings. If tolerability issues arise please refer to section 7.2.3

Please refer to the Schedule of Assessments/Time & Events for details on procedures during the Randomization Phase. There is a visit window of +/- 2 day visit window during the Randomization Phase of the study. It is estimated that approximately 120 subjects will enter this phase of the trial.

4.3.3 Extension Phase (if applicable)

The Extension Phase includes a Baseline Visit; however, that visit is only required if there is a break in dosing two weeks or greater between the Week 8 Visit in the Randomization Phase and the Week 4 visit in the Extension Phase. The Extension Phase also includes a Baseline Visit 1 and Baseline Visit 2; however those visits are only required for subjects who have previously completed the 2 week post-dose visit in the Extension Phase, and who will be reentering the extension phase of open-label treatment beginning at Week 60 through Week 144. Subjects re-entering the extension phase will complete the Baseline 1 visit to confirm that they meet safety eligibility requirements, then return for the Baseline 2 visit, followed by visits scheduled approximately every 12 weeks, as well as laboratory assessments at approximately 4 and 8 weeks after re-starting medication. Thereafter, subjects will undergo visits every 12 weeks up to Week 144 of the Extension Phase (or 192 weeks for continuing subjects). All subjects will undergo a termination visit two weeks after the last dose of study drug.

Please refer to the Schedule of Assessments/Time & Events for details on procedures during the Extension Phase. There is a visit window of +/- 7 days during the Extension Phase of the study.

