4 STUDY PLAN

4.1 Study Design and Duration

BHV4157-201 is a Phase IIb/III, multicenter, randomized, double-blind, 2-arm placebo-controlled parallel-group study designed to assess safety, tolerability, and efficacy in a population of patients with Spinocerebellar Ataxia. Subjects will be randomized to receive placebo (QD) or troriluzole (140 mg QD),

Subjects with SCA3 genotype will be limited to comprise up to approximately 10% so that this most common type of SCA is not over-represented.

Dosing will continue for 8 weeks. Subjects will return to the clinic two weeks after discontinuing study medication for a follow-up safety visit. In addition, subjects completing the Randomization Phase will be offered approximately 192 weeks of open-label treatment as long as the PI believes open-label treatment offers an acceptable risk-benefit profile. Subjects who agree to enter the Extension Phase will not complete the follow-up safety visit and should continue dosing as specified.

Subjects entering the Extension Phase would have their first Extension Visit four weeks after the Week 8 Randomization Phase visit. If there is a delay of two weeks or more in dosing between the Randomization Phase and the Extension Phase, subjects would be required to complete an Extension Baseline Visit. Thereafter, subjects will undergo visits every fourth week through Week 12 of this phase. Then subjects will undergo visits every 12 weeks up to Week 192 of this phase. All subjects will undergo a termination visit two weeks after the last dose of study drug.

Subjects who previously completed the extension phase will be allowed to participate in the expanded extension phase for a total of 144 weeks of open-label administration of troriluzole, provided the PI deems this treatment to present an acceptable risk-benefit profile. Such subjects who have been off of medication for at least 2 weeks, will need additional Baseline Visits followed by visits scheduled approximately every 12 weeks, as well as laboratory assessments at approximately 4 and 8 weeks after re-starting medication. In addition, these subjects will be required to have clinical laboratory assessment results that are not deemed clinically significant, available prior to the Baseline Visit and drawn within 6 weeks prior to that visit. These subjects should not have taken riluzole for at least 12 hours prior to re-starting troriluzole.

[figure not shown]

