For subjects who experienced decline (as defined below) over at least 9 months of treatment with 140 mg troriluzole, the PI may offer an increased dose of 280 mg daily based on anticipated tolerability (e.g., the patient was tolerating the 140 mg dose well). Decline will be defined as demonstration of a 2 point or greater decline from baseline on the SARA scale on two most recent consecutive visits (at least one month apart) accompanied by PI opinion clinical worsening. Patients who do not tolerate 280 mg daily or demonstrate clinically significant lab abnormalities may have their dose adjusted to 140 mg daily. Subjects who increase to 280 mg daily will have lab tests at approximately 4, 8 and 12 weeks after the dose increase, then no less often that approximately every 12 weeks. Subjects who are given a trial

of 280 mg daily troriluzole will require additional clinical lab assessments (LFTs) at approximately 4 and 8 weeks after starting the increased dosing. For subjects who were tolerating 140 mg without adverse effects, the dose increase may occur at the usual dosing time. Some subjects may better tolerate dosing at bedtime to minimize any impact of sedation. In addition, the PI may split doses (twice daily) if adverse events suggest that this could enhance tolerability. Dosing regimen should be recorded in the CRF.

Subjects will be assessed at clinic visits per the Schedule of Assessments/Time & Events.

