¹ Baseline visit for the Extension Phase is *only required* if there is an extended break (≥2 weeks) in dosing between the Randomization and Extension Phases.

Χ

Χ

Х

Х

X

Χ

Χ

Dispense Study Drug

Drug Accountability

² Subjects will be provided with pregnancy tests to take in between every 3-month office visit. Subjects should be instructed to contact if they become pregnant at any time during the study.

³, Subjects whose dose is increased to 280 mg daily will require LFT tests approximately 4 and 8 weeks after the increase and then approximately every 12 weeks thereafter

Table 4. Schedule of Assessments and Events - 144-Week Expanded Extension Phase (continuing subjects)

	Exp.Ext. Wk 60	Exp. Ext. Wk 72	Exp. Ext. Wk 84	Exp. Ext. Wk 96 or early discontinuation visit (less than or equal to EE Wk 96)
Visit	Visit 7	Visit 8	Visit 9	Visit 10
Eligibility Assessments				
Neurological Exam		Х		X
Pregnancy Test for WOCBP (serum)		X		X
¹ Pregnancy Test for WOCBP (urine)	×		X	
Safety Assessments				
Laboratory Assessments including urinalysis		X		X
² Lab: LFT tests only (ALT, AST, BILI, GGT)	X		Х	
Physical Exam		X		X
Physical Measurements	Х	Х	Х	Х
Vital Signs	Х	Х	Х	Х
12-Lead ECG		X		X
Concomitant Medication Review	Х	Х	X	х
Adverse Event Assessments	X	X	X	×
Sheehan Suicidality Tracking Scale (Sheehan STS)	х	х	Х	х
* Clinical Outcome Assessment				
SARA	Х	X	Х	X
Clinical Drug Supply				
Dispense Study Drug	Х	Х	Х	
Drug Accountability	X	Х	Х	Х

⁴ Informed Consent for continuing subjects entering the expanded extension phase will be obtained at next scheduled visit. Visit window is +/- 7 days during the extension phase.

	EE Wk108	EE Wk 120	EE Wk 132	EE Wk 144
Visit	Visit 11	Visit 12	Visit 13	Visit 14
Eligibility Assessments				
Neurological Exam		Х		Х
³ Pregnancy Test for WOCBP (serum)	Х	х	Х	X
Safety Assessments				
^{2, 3} Lab: LFT tests only (ALT, AST, BILI)	Х	х	Х	×
Physical Exam		Х		Х
Physical Measurements	Х	Х	Х	Х
Vital Signs	Х	Х	Χ	X
12-Lead ECG		X		X
Concomitant Medication Review	X	X	X	X
Adverse Event Assessments	Х	х	Х	х
Sheehan Suicidality Tracking Scale (Sheehan STS)	Х	х	Х	Х
Clinical Outcome Assessments				
SARA	Х	Х	Χ	X
Clinical Drug Supply				
Dispense Study Drug ⁴	Х	Х	X	
Drug Accountability	X	X	Χ	X

	EE Wk 156	EE Wk 168	EE Wk 180	EE Wk 192 or Early Discontinuation	EE 2-Wk Post Last Dose
Visit	Visit 15	Visit 16	Visit 17	Visit 18	Visit 19
Eligibility Assessments					
Neurological Exam		Х		Х	
³ Pregnancy Test for WOCBP (serum)	×	Х	Х	x	
Safety Assessments					

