^{2, 3} Lab: LFT tests only (ALT, AST, BILI)	×	Х	Х	x	X
Physical Exam		Х		Х	
Physical Measurements	Х	Х	Х	X	
Vital Signs	Х	Х	Х	X	
12-Lead ECG		Х		X	
Concomitant Medication Review	×	×	×	x	x
Adverse Event Assessments	Х	Х	Х	Х	Х
Sheehan Suicidality Tracking Scale (Sheehan STS)	х	х	х	х	Х
Clinical Outcome Assessments					
SARA	Х	Х	Х	X	Х
Clinical Drug Supply					
Dispense Study Drug ⁴	Х	Х	Х		
Drug Accountability	Х	Х	Х	X	

¹ Subjects will be provided with pregnancy tests to take in between every 3-month office visit. Subjects should be instructed to contact if they become pregnant at any time during the study. Pregnancy testing in between visits is not required EE Week 108 through EE 2-Week Post Dose.

Visit window is +/- 7 days during the extension phase.

² Subjects whose dose is increased to 280 mg daily will require LFT tests approximately 4 and 8 weeks after the increase and then approximately every 12 weeks thereafter

³ Lab will not be done by a Central Lab and must be done at local lab.

⁴ If the study site needs to send drug overnight via certified and tracked courier and this is acceptable to the institution because a visit is absolutely not possible because of the COVID-19 pandemic, this is permissible per study. The sponsor should be consulted prior to shipping drug.

Table 5. Schedule of Assessments and Events – 144 -Week Expanded Extension Phase (returning subjects)

	1							
	¹ Baseline Visit 1	² Baseline Visit 2	Exp.Ext. Wk 4	Exp. Ext. Wk 8	Exp. Ext. Wk 12	Exp. Ext. Wk 24	Exp. Ext. Wk 36	Exp. Ext. Wk 48 or early discontinuation (less than or equal to EE Wk 48)
Visit	Visit EE1	Visit EE2	Visit EE3	Visit EE4	Visit EE5	Visit EE6	Visit EE7	Visit EE8
Eligibility Assessments								
Informed Consent	Х							
⁵ Neurological Exam	X					X		X
Pregnancy Test for WOCBP (serum)						X		X
³ Pregnancy Test for WOCBP (urine)	Х				Х		Х	
Safety Assessments								
⁶ Laboratory Assessments including	х	х				X		X
⁴ Lab: LFT tests only (ALT, AST, BILI, GGT)			Х	X	Х		Х	
Physical Exam	X					X		X
Physical Measurements	Х				Х	Х	Х	Х
Vital Signs	Х				Х	Х	Х	Х
12-Lead ECG						X		X
Concomitant Medication Review	х				Х	Х	×	×
Adverse Event Assessments					х	x	x	×
Sheehan Suicidality Tracking Scale (Sheehan STS)	X				Х	х	Х	X
* Clinical Outcome Assessment								
SARA		Х			Х	X	Х	X
Clinical Drug Supply								
Dispense Study Drug		Х			Х	Х	Х	
Drug Accountability					X	Х	Х	Х
	L	1	l		1	l		l

			1		•

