6.2.4 Laboratory Assessments

Laboratory testing will include the following:

- a) Hematology: hemoglobin, hematocrit, platelets, CBC with differential and absolute neutrophil count
- b) Serum Chemistry: sodium, potassium, chloride, calcium, ALT, AST, LDH, alkaline phosphatase, GGT, phosphorous, bicarbonate, CPK, total protein, albumin, total bilirubin (if greater than 2 mg/dl bilirubin will be fractionated), glucose, creatinine, BUN, uric acid, and pregnancy testing (WOCBP). Additionally, at screening, total cholesterol, LDL, HDL, triglycerides, folate, HbA1C, P-Amylase or Lipase, TSH, and T4:
- c) Urinalysis: macroscopic examination, pH, specific gravity, ketones, nitrites, urobilinogen, leukocyte esterase, protein, creatinine, glucose, and occult blood will be performed during the scheduled visits as specified in the Schedule of Assessments/Time & Events and as medically necessary. If blood, protein, or leukocytes, are positive microscopic examination will be performed on abnormal findings;
- d) Urine pregnancy tests will be performed 72 hours prior to dosing at Baseline, at study visits where lab assessments are not performed, or at the discretion of the Investigator;
- e) HBsAg, HCV and HIV antibody detection will be performed at screening.

Any lab value outside of the normal range must be brought to the attention of a physician (Investigator or Sub-Investigator) at the site. The Investigator will indicate whether or not a flagged value is of clinical significance. In addition, if warranted repeat labs can be drawn. Any local lab results that are out of range must be brought to the attention of the Biohaven Medical Monitor.

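### For returning subjects, Table 5 schedules no adverse-event review before Week 12, no ECG at restart and no pregnancy test at the dispensing visit, and so does not match Table 3

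*Protocol*

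**What the plan says.** Returning subjects are those who finished the first Extension Phase, stopped drug and re-enter for the Expanded Extension. Protocol Section 4.3.3 gives the purpose of their first visit: "Subjects re-entering the extension phase will complete the Baseline 1 visit to confirm that they meet safety eligibility requirements". They then return for Baseline 2, "followed by visits scheduled approximately every 12 weeks, as well as laboratory assessments at approximately 4 and 8 weeks after re-starting medication". Section 4.1 describes the same pattern for subjects off medication for at least 2 weeks.

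Table 5 carries this out. Drug is first dispensed at Baseline 2. The row headed "Adverse Event Assessments" is blank at Baseline 1, Baseline 2, Week 4 and Week 8.

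Table 3 covers restart between the Randomization and first Extension Phases. Its Baseline Visit is needed only "if there is an extended break (≥2 weeks) in dosing between the Randomization and Extension Phases", and it marks adverse events, ECG, and serum and urine pregnancy tests.

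Two other places bear on this. Section 6.2.4(d) says: "Urine pregnancy tests will be performed 72 hours prior to dosing at Baseline". Section 4.1 says of the higher dose: "Patients who do not tolerate 280 mg daily or demonstrate clinically significant lab abnormalities may have their dose adjusted to 140 mg daily". Sections 4.1 and 7.2 also let the investigator move dosing to bedtime or split it in response to adverse events.

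**The concern.** The protocol has two restart schedules with the same minimum dosing break, and they differ in what is checked. The one for returning subjects leaves out adverse-event and concomitant-medication review at the two early contacts it already has. It schedules no ECG at either baseline and marks no pregnancy test at the visit where drug is handed out. No reason for the difference appears in the text.

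Three things are at stake.

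- **Early tolerability.** Dose timing, splitting and reduction depend on tolerability or adverse events, but no scheduled review feeds those decisions in the first 12 weeks. Section 8 allows adverse events to be volunteered or drawn out by open questioning; without a scheduled review, the second route has no set occasion before Week 12.
- **Oversight.** Section 10.1 states that there is no data monitoring committee and relies on the sites to monitor safety.
- **Pregnancy.** Section 1.1.7 says that the drug has not been studied for effects on fertility or fetal development.

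**Working it through.** No stated figure needs reproducing. The check is a row-by-row comparison of the two tables, up to Week 48 in each.

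| Row | Table 3 (baseline after a break) | Table 5 (returning subjects) |
|---|---|---|
| Adverse events | Baseline, Weeks 4, 8, 12, 24, 36, 48 | Weeks 12, 24, 36, 48 |
| Concomitant medication | Baseline, Weeks 4, 8, 12, 24, 36, 48 | Baseline 1, Weeks 12, 24, 36, 48 |
| ECG | Baseline, Weeks 24, 48 | Weeks 24, 48 |
| Serum pregnancy test | Baseline, Weeks 24, 48 | Weeks 24, 48 |
| Urine pregnancy test | Baseline, Weeks 4, 8, 12, 36 | Baseline 1, Weeks 12, 36 |
| Liver function tests only | Weeks 4, 8, 12, 36 | Weeks 4, 8, 12, 36 |

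Table 5 marks dispensing at Baseline 2 and Weeks 12, 24 and 36.

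**Time from restart to first scheduled check**

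- Adverse events, Table 5: 12 × 7 = 84 days. With the ±7-day visit window, 77 to 91 days.
- Adverse events on drug, Table 3: 4 × 7 = 28 days, besides the review at Baseline.
- ECG, Table 5: 24 × 7 = 168 days (161 to 175 with the window). Table 3: at Baseline.

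**Adverse-event reviews on drug in the first 12 weeks.** Table 3 has three (Weeks 4, 8, 12). Table 5 has one (Week 12), although it also has three contacts in that time. At Weeks 4 and 8 blood is drawn for liver function tests and nothing else is marked.

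**Pregnancy test at restart**

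1. Table 5 marks one pre-dose test, by urine at Baseline 1. Neither pregnancy row is marked at Baseline 2.
2. Footnotes 5 and 6 of Table 5 require the neurological exam and safety laboratory tests if Baseline 2 falls more than 7 days after Baseline 1. Neither names a pregnancy test.
3. Section 6.2.4(b) lists pregnancy testing within serum chemistry, so repeat laboratory tests may include one. But the serum pregnancy row of Table 5 is blank at both baselines.
4. Section 6.2.4(d) sets 72 hours before dosing at Baseline. The Table 2 instruction ties that interval to Visit 2 of the Randomization Phase. Whether it also covers the returning-subject baseline is not stated.

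**Earlier ECGs.** Table 2 schedules ECGs at Screening and Week 8, and Table 3 at Extension Weeks 24 and 48. The last scheduled ECG before restart therefore belongs to the first Extension Phase and predates the break.

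**The case against.** The other side has good points, and several stronger readings fail.

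- **Age of the pregnancy test.** Section 4.1 wants laboratory results "drawn within 6 weeks prior to that visit", and a reader might infer that the pregnancy test may be six weeks old at dosing. The text does not support this: the window governs laboratory results, footnote 6 calls for safety laboratory tests after 7 days, and no passage sets a maximum age for the urine test. If Section 6.2.4(d) covers every baseline, only a table mark is missing.
- **ECG.** A reader might infer that ECG changes after restart have nothing to be compared with. Earlier ECGs exist, and the baseline in SAP Section 4.8 is in any case the visit before Extension Visit 1. What is missing is a fresh ECG at restart.
- **Attribution.** It is tempting to say that events from the gap cannot be separated from events on drug. SAP Section 4.8.2 classifies events by start date, so they can be. The weakness is that, at Week 12, the date of an event not already reported rests on memory.
- **Blank cells before dosing.** Sections 8 and 8.2.1 begin non-serious event collection at the start of study drug, and Section 8.1.3 collects serious events from consent. The empty adverse-event cells at the two baselines are consistent with that. The Week 4 and Week 8 blanks are not explained by it.
- **Length of break.** A reader might say that the longer break gets fewer checks. Both baselines share a minimum of 2 weeks, so the comparison is between equal minimum breaks.
- **Different populations.** Table 3 includes former placebo subjects meeting the drug for the first time, while Table 5 subjects have completed open-label treatment. A lighter schedule could be defended on that ground, but the protocol does not do so.
- **280 mg at restart.** No passage says that the higher dose may begin on the restart day. The text does not exclude it for a returning subject who met the decline criterion, and no more can be said. Continuing subjects whose dose is raised also have added contacts for liver tests only (Table 4, footnote 2).

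**Conclusion.** The point holds as a mismatch between schedules. After restart, Table 5 gives one scheduled adverse-event review in 12 weeks against three in Table 3, the first at 84 days rather than 28. Concomitant medication is likewise not reviewed between Baseline 1 and Week 12. No ECG is scheduled at restart, and no pregnancy test is marked at the dispensing visit, where the reach of Section 6.2.4(d) is unclear.

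The effect is on how completely early non-serious events are captured in the Expanded Extension, and on the information available for dosing decisions that the protocol ties to tolerability. Serious and volunteered events are still collected, and the 8-week randomized comparison is unaffected.

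This rests on reading blank cells as assessments not scheduled. Section 4.3.3, with laboratory assessments alone at about Weeks 4 and 8, supports that reading for the adverse-event and concomitant-medication rows. The stray symbols in the ECG row of Table 3 at Weeks 4, 8, 12 and 36 are read as blanks; its Baseline mark does not depend on this.

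**What to change.** Reconcile Table 5 with Table 3, Section 6.2.4(d), and the tolerability-dependent dosing text in Sections 4.1 and 7.2. Three items need a stated decision:

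1. The adverse-event and concomitant-medication rows at the Week 4 and Week 8 contacts, which already take place.
2. The ECG row at restart.
3. The pregnancy-test rows at Baseline 2, including whether Section 6.2.4(d) covers returning subjects and whether the repeat in footnote 6 includes a pregnancy test.

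The sponsor decides which schedule applies. If the difference from Table 3 is intended, a sentence giving the reason would settle it. For subjects who have already restarted, the study report should say how adverse events in the first 12 weeks were ascertained.

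The cost is an amendment to the schedule of assessments. If review is added at Weeks 4 and 8, it uses existing contacts and takes little site time.

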4.4 Post Study Access to Therapy (if applicable)

There is an extension phase of this trial for up to 192 weeks (144 weeks for returning subjects) as described in section 4.3.3. No other study drug access is available after the extension.

5 POPULATION

5.1 Number of Subjects

Approximately 120 subjects are expected to be randomized in this study.

5.2 Inclusion Criteria

1. **Informed Consent**

[figure not shown]
a. Subjects (or legally acceptable representative as required by the IRB/IEC) must provide a written signed informed consent form/forms (IRB/EC specific) prior to the initiation of any protocol required procedures.

2. Age and Sex

a. Male and female outpatient subjects between the ages of 18 - 75, inclusive

3. Target Population

a. Subjects with a known or suspected diagnosis of the following specific hereditary ataxias: SCA1, SCA2, SCA3, SCA6, SCA7, SCA8 and SCA10;

- b. Ability to ambulate 8 meters without assistance (canes and other devices allowed);
- c. Screening total SARA total score ≥8;
- d. Score of ≥ 2 on gait subsection of the SARA;
- e. Determined by the investigator to be medically stable at Baseline/randomization as assessed by medical history, physical examination, laboratory test results, and electrocardiogram testing. Subjects must be physically able and expected to complete the trial as designed;

5.3 Exclusion Criteria

1. Target Disease Exceptions

- a. Any medical condition other than one of the hereditary ataxias specified in the inclusion criteria that could predominantly explain or contribute significantly to the subjects' symptoms of ataxia (for example, alcoholism, vitamin deficiencies, multiple sclerosis, vascular disease, tumors, paraneoplastic disease, head injury, idiopathic late onset ataxia, multisystem atrophy) or that can confound assessment of ataxia symptoms (for example, stroke, arthritis);
- b. MMSE score < 24;

d. SARA total score of > 30 points at screening; Subjects may not have started physical or occupational therapy within one month of screening and are not expected to start such therapy during the randomization phase.

[figure not shown]

[figure not shown]
2. Medical History Exclusions

 a. Clinical history of stroke. Note: Subjects with a history of transient ischemic attack (TIA) may be enrolled, if it occurred at least 3 months prior to screening and the subject is prescribed appropriate treatment [e.g., platelet aggregation inhibitors];

c. Active liver disease or a history of hepatic intolerance to medications that in the investigator's judgment, is medically significant;

[figure not shown]

